1. INTRODUCTION

1.1. Disease Overview

Alnylam Pharmaceuticals is developing ALN-GO1, a synthetic, small interfering RNA (siRNA) therapeutic directed against hydroxyacid oxidase 1 (HAO1) messenger RNA (mRNA), which is covalently linked to a ligand containing 3, N-acetylgalactosamine residues. The proposed indication for ALN-GO1 is the treatment of Primary Hyperoxaluria Type 1 (PH1).

PH1 is a rare, autosomal recessively inherited disease characterized by excessive production of oxalate and consequent hyperoxaluria. Given the relative insolubility of oxalate, it crystallizes in the urinary tract, primarily as calcium oxalate. This results in recurrent nephrolithiasis and/or nephrocalcinosis, with progressive renal disease leading to renal failure.[1] As renal function declines, calcium oxalate is deposited systemically, with consequent end organ damage. This stage of the disease, called systemic oxalosis, arises when the glomerular filtration rate (GFR) has declined to below 30 to 45 mL/min per 1.73 m². [1]

PH1 is caused by mutations in both alleles of the alanine glyoxylate aminotransferase (AGXT) gene, which encodes the liver peroxisomal enzyme alanine-glyoxylate aminotransferase (AGT). Over 150 mutations in AGXT have been described. There are broad genotype–phenotype associations, notably in the responsiveness of disease caused by some mutations, to treatment with pyridoxine (vitamin B6). However, disease phenotype can be highly variable, including the responsiveness to vitamin B6 treatment, even within families.[2]

Given the rarity and heterogeneity of PH1, many patients go undiagnosed for years after the initial clinical manifestations of the disease. The incidence of PH1 is approximately 1 in 120,000 live births, and the prevalence is 1 to 3 per million in North America and Europe.[1-3] The disease is more prevalent in areas where consanguineous marriages are common, especially in the Middle East and Northern Africa.[4, 5]

PH1 is primarily a pediatric disease, with symptoms first appearing in approximately half (48.6%) of the patients in the Rare Kidney Stone Consortium Primary Hyperoxaluria Registry between birth and four years of age. Approximately three-quarters of patients (74.7%) showed signs or symptoms before the age of 15 and 83.5% showed symptoms before 20 years of age. In comparison, only 16.5% of patients first displayed symptoms after age 20. Additionally, nearly one third (29.9%) of patients were diagnosed between birth and four years of age and two-thirds (66%) were diagnosed before 20 years of age. [Rare Kidney Stone Consortium Primary Hyperoxaluria. Available from: <http://rarekidneystones.org/hyperoxaluria/>, accessed on 25 September 2015] The majority of patients are, therefore, diagnosed as children, and consequently, are more likely to have some preservation of renal function at time of diagnosis.

Most PH1 patients exhibit urinary oxalate excretion greater than 2-fold the upper limit of normal (ULN), although patients with severely compromised renal function may have lower excretion rates. PH1 is definitively diagnosed by gene sequencing to detect pathological mutations in AGXT, or by evaluation of AGT enzymatic activity in liver tissue obtained by biopsy.

Currently, there are no approved therapies for the treatment of PH1. Disease management is based on supportive measures, including high fluid intake, potassium citrate (to increase urinary oxalate solubility), Vitamin B6, and treatment of complications such as urinary tract stones and infections. Dietary modification plays a minor role in treatment since endogenous oxalate

production far exceeds dietary intake. Patients progressing to, or presenting with end-stage renal disease (ESRD) require intense kidney dialysis. However, dialysis, day and night, 6 days per week, may be inadequate to effectively offload accumulating oxalate.[6] Combined liver/kidney transplantation offers potentially curative therapy, but with limited availability, the attendant medical risks, and intense use of health care resources. Therefore, there is a high unmet medical need for additional treatments for patients with PH1. The deterioration of renal function that occurs in PH1 disease indicates the importance of investigating potentially disease-modifying interventions as early as possible after diagnosis.

1.2. ALN-GO1

1.2.1. ALN-GO1 Description

ALN-GO1 (containing siRNA drug substance ALN-65585) is an investigational medicinal product that comprises a synthetic siRNA that specifically targets the mRNA of the HAO1 gene which encodes glycolate oxidase (GO).

1.2.2. Rationale for ALN-GO1 for the Treatment of Primary Hyperoxaluria Type 1

GO, a hepatic enzyme upstream of AGT, mediates the oxidation of glycolate to glyoxylate, which then is further metabolized to oxalate. Suppression of GO by ALN-GO1 is expected to reduce the production of oxalate, while increasing the generation of glycolate. Unlike oxalate, glycolate is highly soluble and readily excreted in the urine. The effective substitution of glycolate for oxalate production is hypothesized to significantly ameliorate the course of PH1 disease. Moreover, the mechanism of action of ALN-GO1 suggests that plasma glycolate could be a biomarker for the inhibition of GO1, serving as a pharmacodynamic (PD) measure of ALN-GO1 activity in healthy subjects.

1.2.3. Nonclinical Data

The pharmacology, safety pharmacology, drug metabolism and pharmacokinetics (PK), and toxicology of ALN-GO1 were evaluated in a series of in vitro and in vivo nonclinical studies.

Nonclinical pharmacology studies include the assessment of in vitro activity of ALN-GO1 in primary hepatocytes from non-human primates (NHP); and in vivo in wild-type (WT) mice deficient in AGXT (a genetic model of PH1), WT rats, rats with inhibited AGXT activity (an induced model of PH1), and WT NHP. When subcutaneously administered, ALN-GO1 demonstrated potent, dose-dependent pharmacologic activity, resulting in reduced liver HAO1 mRNA levels with the expected increases in plasma glycolate levels in WT and diseased animals as well as subsequent reductions in urinary oxalate in diseased animals. Modest increases (approximately 1.5-fold) in plasma glycolate levels were observed in NHP treated with 1 mg/kg of ALN-GO1 subcutaneously administered every 4 weeks, the lowest dose studied with a 4-week dosing interval.

Good Laboratory Practice (GLP) -compliant toxicology studies were performed in rats at 0, 5, 15, or 50 mg/kg weekly or 50 mg/kg monthly and in NHP at 0, 10, 30, and 100 mg/kg weekly or 100 mg/kg monthly, with treatment administered for 8 weeks. The no observed adverse effect levels (NOAEL) were 50 mg/kg in rats and 100 mg/kg in NHP (Table 5).

Genetic toxicity studies (bacterial reverse mutation, human peripheral blood lymphocyte chromosomal aberrations, and rat bone marrow micronucleus assays) were all negative based on industry guidelines.[7]

In summary, nonclinical studies have shown pharmacological activity in NHP at doses as low as 1.0 mg/kg, while doses as high as 50 mg/kg and 100 mg/kg in rat and NHP, respectively, have resulted in no adverse effects after 8 weeks of treatment. These data provide the justification for the starting dose for administration in this clinical study.

1.3. Study Design Rationale

This is a randomized, single-blind, placebo-controlled, multi-center Phase 1/2 single-ascending dose (SAD) and multiple-ascending dose (MAD) study designed to evaluate the safety, tolerability, PK, and PD of subcutaneously administered ALN-GO1 in healthy adult subjects and in adult and pediatric patients with PH1. The primary objective of the study is to evaluate the safety and tolerability of single-ascending doses of ALN-GO1 in healthy adult subjects and multiple-ascending doses of ALN-GO1 in patients with PH1. Secondary and exploratory objectives of the study include the characterization of plasma and urine PK for ALN-GO1 and the evaluation of the PD effect of ALN-GO1, including glycolate and oxalate concentration and excretion.

Part B of this study will be implemented as a delayed start study; all patients will receive active study drug. Patients initially randomized to receive placebo will transition to active study drug; thus, additional safety data will be collected from patients transitioning from placebo to active study drug. The design allows for evaluation of safety and PD data at multiple dose levels in healthy subjects before initiating dosing in patients with PH1. This will permit more efficient dose selection in patients, given the rarity of the disease, and limits exposure of patients to ALN-GO1 as safety is being assessed.

1.4. Dose Rationale

The proposed starting dose in healthy subjects in Part A of this study is 0.3 mg/kg. Data in NHP suggest that this dose will have a low level of pharmacologic activity, while NOAELs determined in rat and NHP 8-week GLP toxicity studies indicate a wide margin of safety. While it is expected that nonclinical PD and toxicity will translate to humans on a body weight (mg/kg) basis, a more conservative approach for determining the starting dose was calculated by converting the NOAEL in the rat and NHP to a human equivalent dose (HED) using body surface area (BSA; mg/m²). Using BSA conversions, safety margins for the clinical starting dose of 0.3 mg/kg were 26.7-fold and 106.7-fold in the rat and NHP, respectively, whether study drug was administered weekly or every 4 weeks. Collectively, the results of the ALN-GO1 nonclinical and pharmacological studies support the starting dose of 0.3 mg/kg in this first-in-human study. The starting dose in patients will be the lowest dose determined to have a pharmacological effect in healthy subjects that was also considered safe and well-tolerated.

Table 5: No Observed Adverse Effect Level and Starting Dose Safety Margins

	NOAEL (mg/kg)	HED based on BSA (mg/kg)	Safety margin for proposed starting dose of 0.3 mg/kg (Part A)	
			Based on mg/kg	Based on BSA ^a
Rat (QW×9)	50	8	167-fold	26.7
Rat (Q4W×3)	50	8	167-fold	26.7
NHP (QW×9)	100	32	333-fold	106.7
NHP (Q4W×3)	100	32	333-fold	106.7

Abbreviations: BSA=body surface area; HED=human equivalent dose; NHP=nonhuman primates; NOAEL=no observed adverse effect level; Q=every; W=week.

^a BSA margin calculated using species-scaled conversion assumptions.[8]

Doses were selected for this study in accordance with Committee for Medicinal Products for Human Use (CHMP) guidelines on Risk Identification and Mitigation in first-in-human clinical studies (EMA/CHMP/SWP/28367/07).

Preliminary data from Part A suggest that ALN-GO1 is well-tolerated and support selection of the starting dose for the first cohort of Part B of study ALN-GO1-001. The Part B starting dose is 1.0 mg/kg, administered every 28 days, the lowest dose determined to have a pharmacological effect in healthy subjects in Part A that was also considered well-tolerated. The starting dose in Part B is based on data derived from Part A and recommended by the Safety Review Committee (SRC). Additional cohorts may be enrolled at higher, lower, or intermediate dose levels, but will not exceed the maximum administered dose of 6 mg/kg, and will follow the protocol-specified dose escalation criteria.

1.5. Benefit-Risk Assessment

ALN-GO1 is designed to reduce hepatic production of oxalate. The potential benefit of this treatment is the amelioration of the clinical course of PH1 in patients across the spectrum of disease, irrespective of age and disease stage; however, patients with PH1 in this study may not receive treatment for a sufficient duration, or at an adequate dose, to experience clinical benefit. There is no benefit for healthy subjects participating in this clinical study of ALN-GO1. The potential risks of ALN-GO1 include pathway- and disease-specific risks, and non-specific, off-target risks.

Reduction of GO is expected to lead to reduction in hepatic oxalate production at the expense of increased glycolate, an organic acid. Therefore, study drug-induced increases in plasma and urine glycolate levels are anticipated in both healthy subjects and patients administered ALN-GO1. Since elevated levels of this organic acid are expected to be readily buffered, and its high solubility is not expected to result in crystallization in the urinary tract, the potential risk of increased glycolate production is considered low. Importantly, no toxicity has been observed in NHP pharmacology and toxicology studies, where profound suppression of hepatic GO, with associated increases in plasma glycolate levels, has been demonstrated. In particular,

maintenance of normal serum bicarbonate levels in these animals indicates that there is no evidence of acidosis. Finally, a recent clinical case study described a child with an incidentally discovered homozygous defect in HAO1, the gene encoding GO. The patient exhibited marked elevations of urine glycolate, but no associated metabolic abnormalities and normal renal and hepatic function.[9]

The potential negative consequences of ALN-GO1 administration to patients with impaired renal function, including those with end stage renal disease (ESRD), are considered low. ALN-GO1, in common with other Sponsor-developed RNAi compounds, is conjugated to N-acetyl galactosamine (GalNAc) to enable rapid and specific uptake by hepatocytes via the asialoglycoprotein receptor. Clinically effective doses of ALN-GO1 are not expected to saturate this receptor-mediated uptake or to result in enhanced extra-hepatic uptake or significant extra-hepatic exposure via accumulation; however, only patients with relatively well-preserved renal function are eligible to participate in this study.

PH1 is primarily a pediatric disease, with predominantly early childhood expression of symptoms, an early age at diagnosis, and a decline in renal function with increasing age in childhood through adulthood. [Rare Kidney Stone Consortium Primary Hyperoxaluria. Available from: <http://rarekidneystones.org/hyperoxaluria/>, accessed on 25 September 2015] The consequence is that early treatment is required to gain the greatest potential benefit and prevent loss of renal function as these patients age. Systemic oxalosis, resulting from over production combined with insufficient dialytic clearance of oxalate, is the most devastating complication of PH1 and is not prevented or effectively treated by dialysis. Liver/kidney transplantation is considered curative, but has high cost, high morbidity, and relatively low availability. Children with relatively well-preserved renal function are more prevalent than adults and are the primary target population for development of ALN-GO1. For this reason, children are included in the population for evaluation in this study.

This study is designed such that safety data in healthy adult subjects will be evaluated at dose levels higher than proposed for the starting dose in patients, including those as young as 6 years of age. Since the intended lowest dose for administration in patients will have been demonstrated to result in increased plasma glycolate concentration, a marker of the PD effect of ALN-GO1, and adequate safety in healthy subjects, the initial starting dose in patients is expected to be a potentially active dose of ALN-GO1.

Although the study includes a placebo control, all patients initially assigned to placebo will be administered active treatment via a delayed start study design. Study assessments and visits have been reduced as much as possible to minimize the burden of the study on children without risking patient safety. The potential benefit to children enrolled in this study includes possible reduction in oxalate production during the study period, which may have a temporarily ameliorating effect on their disease. In addition, experience in children with this disease under carefully controlled conditions will provide data that may enhance the future development of this therapeutic.

Important potential risks to healthy subjects and patients include injection site reactions (ISRs). Other potential risks include: embryofetal toxicity, coagulation abnormalities, and liver function test abnormalities. These potential risks have been reduced by the specific inclusion and exclusion criteria incorporated into the selection of healthy subjects as well as for patients with PH1 in this clinical study.

No data are available on the use of ALN-GO1 in pregnancy; however, human mutagenicity is not suggested based on the available nonclinical data (see Investigator's Brochure for further information). Embryofetal risk is limited by requiring that women of childbearing potential (WOCBP) must have a negative pregnancy test, cannot be breast feeding, and must be willing to use a highly effective method of contraception as specified in the protocol. Male subjects/patients are not required to use the contraception measures required for female study subjects/patients. No male contraception is considered to be required.

The occurrence of ISRs will be carefully monitored.

Nonclinical studies in rats showed mild to moderate decreases in fibrinogen and occasionally minimal prolonged prothrombin time without accompanying clinical or microscopic evidence of hemorrhage. This effect is likely species-specific as it was not observed in NHPs and will be monitored via clinical laboratory safety assessments.

As ALN-GO1 is a hepatically-targeted therapeutic, liver function tests will be carefully monitored. Nonclinical data suggest that there is a wide margin between the proposed clinical doses and any hepatic findings in toxicology studies and that any findings can be monitored. The potential non-specific, off-target risk of ALN-GO1 administration is considered to be low, based on nonclinical toxicological assessment of this molecule and accumulating experience with this RNA interference (RNAi) therapeutics platform.

During the course of this study, safety will be monitored by study Investigators, the Sponsor Medical Monitor, and a SRC. The initial dose level for administration in the MAD part of the study will have been previously shown to be safe, tolerable, and pharmacologically active based on SRC review of safety and PD data from the SAD part of the study. Stopping rules have also been designed to protect study participants.

Overall, in this clinical study of ALN-GO1, the risk to healthy subjects is considered low and the benefit/risk assessment is favorable in patients with PH1. Moreover, since evaluation of safety and PD effects in children will be important in the design of future studies, it is considered important and appropriate to enroll children in the current study.

The complete summary of the clinical and nonclinical data relevant to the investigational drug and its study in human subjects is provided in the Investigator's Brochure.

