7.5.6. Clinical Laboratory Assessments

Clinical laboratory tests will be evaluated as noted in the Schedule of Assessments. In the event of an unexplained clinically relevant abnormal laboratory test occurring after study drug administration, the test should be repeated and followed up at the discretion of the Investigator until it has returned to the normal range or stabilized, and/or a diagnosis is made to adequately explain the abnormality.

Hematology

Complete blood count with differential

Serum Chemistry

Sodium

Potassium

BUN

Phosphate

Creatinine and eGFR calculation (using the MDRD or Schwartz formula depending on age)

Albumin

Uric acid

Calcium

Total protein

Carbon dioxide/bicarbonate

Glucose

Chloride

Cardiac Enzyme

Troponin I

Liver Function Tests

AST

ALP

ALT

Bilirubin (total and direct)

Coagulation Panel

Prothrombin time

International Normalized Ratio

Activated partial thromboplastin time

Urinalysis

Visual inspection for appearance and color	Bilirubin
pH (dipstick)	Nitrite
Specific gravity	RBCs
Ketones	Urobilinogen
Albumin (optional)	Leukocytes
Glucose	Microscopy (if clinically indicated)
Protein	

Immunogenicity

Antidrug Antibodies

Pregnancy Testing (WOCBP only) β -human chorionic gonadotropin

Abbreviations: AST=aspartate transaminase; ALP=alkaline phosphatase; ALT=alanine transaminase; BUN=blood urea nitrogen; eGFR=estimated glomerular filtration rate; MDRD=modification of diet in renal disease; WOCBP=women of child bearing potential.

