6.1.7 Clinical Laboratory Assessments

For both Part A and Part B, clinical laboratory tests will be evaluated at the times indicated in the Schedule of Assessments. Laboratory tests to be collected include:

- Hematology: Complete blood count with differential
- Serum Chemistry: Sodium, blood urea nitrogen (BUN), Creatinine and estimated glomerular filtration rate (eGFR) calculation (using the modification of diet in renal disease or Schwartz formula depending on age), uric acid, total protein, glucose, potassium, phosphate, albumin, calcium, carbon dioxide/bicarbonate, chloride
- Cardiac Enzyme: Troponin I
- Liver Function Tests: aspartate transaminase (AST), alkaline phosphatase (ALT), alkaline phosphatase (ALP), total and direct bilirubin
- Coagulation Panel: Prothrombin Time, Activated partial thromboplastin time, International Normalized Ratio
- Urinalysis: Visual inspection of appearance and color, pH (dipstick), specific gravity, Ketones, Albumin (optional), Glucose, Protein, Bilirubin, Nitrite, RBCs, Urobilinogen, Leukocytes, Microscopy (if clinically indicated)
- Immunogenicity: Anti-drug antibodies
- Pregnancy Testing: β-human chorionic gonadotropin (women of child bearing potential only). Serum testing will be performed at screening or menarche, and urinary screening thereafter.

The eGFR (in mL/min/1.73m²) will be calculated from serum creatinine (SCr) based on the Modification of Diet in Renal Disease (MDRD) formula for patients \geq 18 years of age and the Schwartz Bedside Formula for subjects \leq 18 years of age at enrollment.

MDRD Formula

Conventional units:

```
eGFR (mL/min/1.73m^2) = 175 \times (S_{Cr}[mg/dL])^{-1.154} \times (age)^{-0.203} \times (0.742, if female), or \times (1.212, if African American)
```

SI units

```
eGFR (mL/min/1.73m^2) = 175 \times (S_{Cr} [\mu mol/dL]/88.4)^{-1.154} \times (age)^{-0.203} \times (0.742, if female), or \times (1.212, if African American)
```

Schwartz Bedside Formula

Conventional units:

```
eGFR (mL/min/1.73m^2) = (.413 \times height [cm]) / Scr (mg/dL)
```

• SI units:

```
eGFR (mL/min/1.73m^2)= (36.2 \times \text{height [cm]})/ \text{Scr} (\mu \text{mol}/\text{dL})
```

All triplicate height measurements at a particular time point will be averaged and the mean will be used in the calculation of the eGFR.

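### Fibrinogen, the larger part of the rat coagulation signal that Protocol 1.5 says will be monitored, is missing from the coagulation panel, so the risk is only partly monitored

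*Protocol*

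**What the plan says.** Protocol 1.5 (Benefit-Risk Assessment) separates one important potential risk, injection site reactions, from a second group: "Other potential risks include: embryofetal toxicity, coagulation abnormalities, and liver function test abnormalities". For coagulation it gives the nonclinical basis, "Nonclinical studies in rats showed mild to moderate decreases in fibrinogen and occasionally minimal prolonged prothrombin time", and notes that no clinical or microscopic hemorrhage accompanied these changes. It then commits to monitoring: "This effect is likely species-specific as it was not observed in NHPs and will be monitored via clinical laboratory safety assessments".

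Protocol 7.5.6 lists the laboratory tests. Its coagulation panel has three entries: "Prothrombin time", "International Normalized Ratio" and "Activated partial thromboplastin time". SAP 6.1.7 repeats them: "Coagulation Panel: Prothrombin Time, Activated partial thromboplastin time, International Normalized Ratio". The laboratory footnotes to the Schedules of Assessments (Table 1 footnote k, Table 2 footnote k, Table 3 footnote j, Table 4 footnote k) refer the reader to Section 7.5.6 for the coagulation tests.

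**The concern.** Section 1.5 promises that the safety laboratory tests will follow an effect whose first-named component is a fibrinogen decrease. The list that should deliver this does not contain fibrinogen. A site that follows the plan exactly will never produce a fibrinogen result.

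Safety and tolerability are the primary objective. The Safety Review Committee (SRC) looks at laboratory data before Part A escalation (Protocol 4.7.1) and at accumulating safety data before each new Part B cohort (4.7.2). Under 7.5.7.2, clinically relevant laboratory findings are recorded as adverse events, but an analyte that is not measured cannot produce one. Part B enrolls children from age 6. An ethics committee or investigator reading Section 1.5 would reasonably think that fibrinogen is being watched.

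**Working it through.** No arithmetic decides this point. The check sets the commitment beside every place where a laboratory test could be specified.

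1. **What is to be monitored.** The Section 1.5 sentence describes one effect with two components in rats: a fibrinogen decrease (mild to moderate) and PT prolongation (occasional and minimal).

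2. **By what means.** The sentence points to the clinical laboratory safety assessments. Those are the tests in Protocol 7.5.6, restated in SAP 6.1.7.

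3. **What those lists contain.**

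| Item | Named in Protocol 1.5 as a rat finding | Protocol 7.5.6 | SAP 6.1.7 |
|---|---|---|---|
| Fibrinogen | Yes | No | No |
| Prothrombin time | Yes | Yes | Yes |
| INR | No | Yes | Yes |
| aPTT | No | Yes | Yes |

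Of the two rat findings, one is covered. Fibrinogen is in 0 of the 2 lists. It is also absent from the hematology, chemistry, liver and urinalysis entries.

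4. **Could it be specified elsewhere?** The schedule footnotes refer to 7.5.6 and add no coagulation test. Fibrinogen otherwise appears only in the Amendment 4 summary of changes, which reproduces the Section 1.5 text. Some exploratory assessments are redacted, but the commitment is to safety laboratory tests, and those lists are not redacted.

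5. **Is the SAP simply out of date?** The summary of changes places the coagulation text in the Amendment 4 update of Section 1.5 (27 June 2017). The SAP is dated 01 November 2017 and states that it is written to Amendment 4. It still lists three tests, so it did not predate the text.

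6. **Can PT stand in for fibrinogen?** By Section 1.5's own description, fibrinogen fell mildly to moderately while PT was prolonged only occasionally and minimally. A fibrinogen fall with little or no PT change fits that pattern, and the present panel could miss it.

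7. **Who is affected going forward?** Planned enrollment is 40 in Part A plus 24 in Part B, which gives 64. Preliminary Part A data had already set the Part B starting dose in Amendment 1 (01 July 2016), before Amendment 4. The group in which a change can still be useful is therefore Part B, up to 24 patients.

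**The case against.** Several points on the other side have force.

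- **The risk is not unmeasured.** A reader might infer that the coagulation risk goes unmonitored. The documents do not support that. The named risk is coagulation abnormalities as a class; PT, one of the two rat findings, is in the panel together with INR and aPTT, and the panel is scheduled in both parts. This stands, and it limits the point to partial monitoring.
- **The animal signal is modest.** There was no hemorrhage, the effect was not seen in non-human primates, and coagulation is not listed as an important risk. The rat no-adverse-effect level was 50 mg/kg, the top dose in the GLP study; the documents do not say whether the fibrinogen change arose in that study. This bears on how likely harm is and supports a lower severity. It does not answer whether the promised monitoring takes place, since the sponsor made the commitment in the same sentence that notes the primate result.
- **Decision rules do not use fibrinogen.** A reader might infer that escalation decisions are compromised. Progression and stopping rules run on CTCAE-graded adverse events, and none is tied to a named coagulation analyte. The supportable statement is only that the SRC's laboratory data would lack fibrinogen.
- **No false conclusion is planned.** The SAP tabulates what was measured and plans no statement that coagulation was unaffected. Testing species-specificity is not among the unredacted objectives. Both points stand.
- **Follow-up of abnormal tests.** Section 7.5.6 requires unexplained, clinically relevant abnormal results to be repeated and followed. This reaches a fibrinogen fall only if it disturbs a test that is in the panel, so it mitigates only in part.
- **Editing the sentence would also remove the contradiction.** This is true, and it is the right remedy where measurement is not possible. Where measurement is still possible, it would resolve the wording by dropping the safety information that the protocol said would be collected.

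**Conclusion.** The plan is wrong as written on one specific point. Section 1.5 states that a two-part effect will be monitored, and the panel in Protocol 7.5.6 and SAP 6.1.7 measures only one part, PT. The omitted part, fibrinogen, is the larger one on the protocol's own description. The prospective scope is Part B, up to 24 patients. A figure of 64 participants is tempting but overstates the reach, because it counts the 40 planned Part A subjects.

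Severity: should fix. No endpoint, analysis set or planned summary becomes invalid, and PT, INR and aPTT data remain usable.

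The conclusion assumes that the protocol's list defines the panel. The Laboratory Manual and Investigator's Brochure were not available. If the Laboratory Manual already includes fibrinogen, the correction reduces to bringing the protocol and SAP lists into line with it.

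**What to change.** Reconcile Protocol 1.5 with Protocol 7.5.6 and SAP 6.1.7:

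1. Add fibrinogen to the coagulation panel in both documents, at the existing Part B clinical laboratory visits. Check any added sample volume beforehand against the pediatric limits in Protocol 7.5.6.4 and Table 13.
2. Let it enter the SAP 7.4.3 change-from-baseline and low/normal/high shift summaries. The signal is a decrease, so the shift to low is the display that matters; the summary relative to the upper limit of normal says little here. Under SAP 4.3.1 and Section 7, a change from baseline needs a value before the first dose, so patients already dosed would contribute actual values only.
3. For participants or visits where fibrinogen was not or cannot be measured, including Part A if it is closed, correct the Section 1.5 sentence to say that only PT, INR and aPTT are monitored.

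Cost: one assay per existing Part B laboratory visit, plus short edits to the protocol, SAP and Laboratory Manual. No visit is added. The documents do not say whether the present coagulation sample is large enough, so a small increase in blood volume is possible. This matters most for the smallest children, for whom some exploratory samples are already optional when limits are exceeded.
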